**Table 13-1. Calculation of Total CDAI Score**

Variable no.	Variable	Variable description	Multiplier
1	Liquid or very soft stool	Daily stool count is summed for 7 days	2
2	Abdominal pain	Sum of 7 days of daily ratings as 0 = none, 1 = mild, 2 = moderate, 3 = severe	5
3	General wellbeing	Sum of 7 days of daily ratings as 0 = generally well, 1 = slightly below par, 2 = poor, 3 = very poor, 4 = terrible	7
4	Complications	Number of listed complications: - Arthritis or arthralgia - Erythema nodosum, pyoderma gangrenosum or aphthous stomatitis - Iritis or uveitis - Anal fissures or fistulae or abscess - Other fistula - Fever over 37.8 C [100 F] during past week	20 each
5	Use of anti-diarrheal medications	Use of diphenoxylate or loperamide or other opiate for diarrhea 0 = No, 1 = Yes	30
6	Abdominal mass	0 = none, 2 = questionable, 5 = definite	10
7	Hematocrit*	Males: 47 – Hct [%] Females: 42 – Hct [%] *Result must be greater than or equal to 0. If negative result enter 0	6 × difference
8	Weight*	Percentage deviation from standard weight (1 – weight / standard weight) × 100 *Limit of -10 (Result must be greater than or equal to -10)	1
CDAI score			TOTAL

CDAI = Crohn’s Disease Activity Index; Hct = hematocrit  
 {[Sandborn 2002](#)}

**Table 13-2. Calculation of PRO2 Components**

Variable no.	Variable	Variable Description
1	Liquid or very soft stool	Mean of the daily (liquid or very soft) stool count for 7 days
2	Abdominal pain	Mean of 7 days of daily ratings as 0 = none, 1 = mild, 2 = moderate, 3 = severe

{Khanna 2015}

Each PRO2 subscore will be rounded to the nearest integer (eg, 2) in the determination of subject eligibility for the study and calculation of endpoints.

**Table 13-3. Calculation of Total PRO2 score**

Variable no.	Variable	Variable Description	Multiplier
1	Liquid or very soft stool	Mean of the daily (liquid or very soft) stool count for 7 days	2
2	Abdominal pain	Mean of 7 days of daily ratings as 0 = none, 1 = mild, 2 = moderate, 3 = severe	5
Total PRO2 scoreg			TOTAL

{Khanna 2015}

The 3 patient-reported outcome components for CDAI (and each subscore for PRO2) are determined using an electronic daily diary, which collects subject reported components directly. Given that the ileocolonoscopy procedure (including protocol-directed and non-protocol-directed procedures) may impact the validity of the diary data, diary data collected 1 day prior to and on the day of the procedure will not be used in the calculation of CDAI and PRO2 subscores for all visits. Those days are called non-evaluable days.

### **Calculation of CDAI and PRO2 Scores at Screening**

Ileocolonoscopy is required to be performed during screening. The calculations of CDAI and PRO2 at screening are specified below:

[figure not shown]
- 1) Define T-Day 1 = subject activation date on the electronic diary device during screening
- 2) Define a 10-day window using T-Day 1 as the anchor date, and the window starts the day after T-Day 1 and ends 10 days after T-Day 1.
- 3) For each CDAI patient-reported outcome component, if there are 7 or more evaluable records within the 10-day window, take the **sum** of the 7 evaluable records closest to T-Day 1. For

each PRO2 component, take the **average** of the 7 evaluable records within the 10-day window closest to T-Day 1.

- a) If there are 4 or more (but less than 7) evaluable records within this 10-day window, the average of the available records will be taken, and then multiplied by 7 for the corresponding CDAI patient-reported component. For the corresponding PRO2 component, the average of the available records will be taken.
- b) If subjects do not have at least 4 evaluable records within this 10-day window, the corresponding CDAI patient-reported component and PRO2 component will not be calculated and will be considered as missing.

A schema of this approach and some examples are included below for further illustration:

**Figure 13-1. Selection of Diary Data for the Calculation at Screening**

**Table 13-4. Calculation of CDAI Patient-Reported Outcome Components and PRO2 Scores at Screening**

Example	Diary Day Looking Forward from subject activation date (T-Day)										Days for Calculation	Sum of 7 Days (CAI Patient-Reported Component)	Average of 7 Days (PRO2)
	2	3	4	5	6	7	8	9	10	11			
Diary Subscore 1	1	2	M	1	2	2	M	0	1	2	2,3,5,6,7,9,10	9.0	1.3
Diary Subscore 2	M	M	1	M	2	1	M	2	M	M	4,6,7,9	10.5	1.5
Diary Subscore 3	2	M	M	0	M	2	M	M	M	M	2,5,7	Missing	Missing
Diary Subscore 4	1	2	1	1	X	IL	3	3	1	2	2,3,4,5,8,9,10	12.0	1.7

M = Missing. IL = Ileocolonoscopy day; X = non-evaluable (due to preparation for ileocolonoscopy). Days are named relative to subject activation date on electronic diary device during screening (T-Day 1). Rounding of subscores into one decimal place is for displaying purpose only. When calculating the total CDAI scores, the subscores will not be rounded.

- 4) For the non-diary components (ie, complications, use of anti-diarrheal medications, abdominal mass, hematocrit, and weight) of the CDAI, in the case of multiple records collected during screening, the value collected on the same date as T-Day 1 will be used; otherwise, the earliest valid value during screening (for re-screened subjects, most recent screening period will be used first before using previous screening period) will be used. If no valid value is available during screening, then the value on Day 1 will be used.
- 5) The CDAI total score at screening is based on a weighted sum (rounded to the nearest integer) of all 8 components (no rounding applied to the subscore for each component when calculating the CDAI total score, but the subscore will be displayed with one decimal place for displaying purpose). The weight (multiplier) of each component is specified in [Table 13-1](#). For example, if the sum of the 7-day scores for abdominal pain is 10, then the abdominal pain CDAI subscore is  $10 \times 5 = 50$ , where 5 is the multiplier for abdominal pain. The CDAI total score will be set to 0 in the case the calculation leads to a CDAI total score of  $< 0$ .
- 6) The PRO2 subscores at screening are based on the calculation of liquid or very soft stool frequency and abdominal pain subscores individually (rounded to the nearest integer).

### **Calculation of CDAI and PRO2 Scores at Post-Screening Visits**

[figure not shown]
The calculations of CDAI and PRO2 scores at post-screening visits are specified below:

- 1) CDAI and PRO2 are not assessed on Day 1 and Week 11 by the study sites, but for baseline (or maintenance baseline) summary purpose, the PRO2 subscore and Total PRO2 score will be calculated for Day 1 and Week 11. Both screening and Day 1 values will be considered for the derivation of Induction baseline for PRO2 subscores and total PRO2 score. Similarly, both Weeks 10 and 11 values will be considered for the derivation of maintenance baseline for PRO2 subscores and total PRO2 score. CDAI at Day 1 and Week 11 will not be calculated, and CDAI at screening will be Induction baseline, and at Week 10 will be maintenance baseline.
- 2) The visit date will be used as the anchor day for post-screening visits. The visit date for each analysis visit will be selected among all scheduled visits and unscheduled visits where CDAI were assessed within the analysis window as defined in Section 3.8.2. For Day 1, the date of visit from the nominal visit Day 1 will be used. Only diary data collected on evaluable days within a 10-day window which starts 10 days prior to the visit date (V-Day 1) and ends on the day prior to V-Day 1 will be used for calculation.
- 3) If there are 7 or more evaluate records within the 10-day window, take the **sum** of the 7 evaluable records closest to V-Day 1 for the corresponding CDAI subject-reported component. For the corresponding PRO2 component, take the **average** of the 7 evaluable records within the 10-day window closest to V-Day 1.
  - a) If there are 4 or more (but less than 7) evaluable records within this 10-day window, the average of the available records will be taken, and then multiplied by 7 for the corresponding CDAI patient-reported component. For the corresponding PRO2 component, the average of the available records will be taken.
  - b) If subjects do not have at least 4 evaluable records within this 10-day window, the corresponding CDAI patient-reported component, and the corresponding PRO2 component will not be calculated and will be considered as missing for that visit.

A schema of this approach and some examples are included below for further explanation:

**Figure 13-2. Selection of Diary Data for the Calculation at Post-Screening Visits**

**Table 13-5. Calculation of CDAI Patient-Reported Outcome Components and PRO2 Scores at Post-Screening Visits**

Example	Diary Day Looking Backwards from Visit Date (V-Day)										Days for Calculation	Sum of 7 Days (CDAI Patient-Reported Component)	Average of 7 Days (PRO2)
	-10	-9	-8	-7	-6	-5	-4	-3	-2	-1			
Diary Subscore 1	1	2	2	M	0	1	2	2	1	X	-2,-3,-4,-5,-6,-8,-9	10.0	1.4
Diary Subscore 2	M	M	1	M	X	IL	2	2	1	M	-2,-3,-4,-8	10.5	1.5
Diary Subscore 3	M	M	1	X	IL	M	M	2	1	M	-2,-3,-8	Missing	Missing
Diary Subscore 4	0	M	2	2	1	0	M	2	X	IL	-3,-5,-6,-7,-8,-10	8.2	1.2

M = Missing; IL = Ileocolonoscopy day; X = non-evaluable (due to preparation for ileocolonoscopy).

Days are named relative to visit date (V-Day 1), where V-Day -1 is the day prior to V-Day 1.

Rounding of subscores into one decimal place is for displaying purpose only. When calculating the total CDAI scores, the subscores will not be rounded.

- 4) The CDAI total score for a specific visit is based on a weighted sum (rounded to the nearest integer) of all 8 components. The CDAI total score will be set to 0 in the case the calculation leads to a CDAI total score of < 0. Each component will be selected within the analysis window as defined in
- 5) If subjects have 3 or more of the 8 CDAI components missing, then the subjects will be considered as having insufficient data to determine response status and their total CDAI score will be considered missing. If at least 1 out of the 6 complications under the complication component is missing, then the complication component will be considered missing.

- a) If subjects have 1 or 2 CDAI components missing, then the missing component will be imputed by the LOCF method using the previous valid component score calculated from the most recent analysis visit (ie, use the component score from Week 6 for missing component at Week 10, or use the component score from Week 50 for missing component at Week 58. Scores from other post Induction baseline visits will not be used). If the component score from the most recent analysis visit is also missing, the missing value will be imputed with the corresponding component score at Induction baseline.

The PRO2 subscores for a specific visit are based on the evaluation of liquid or very soft stool frequency and abdominal pain subscores individually (rounded to the nearest integer) within the analysis window as defined in Section 3.8.2. If either subscore is missing, no imputation will be done and the subject will be considered as having insufficient data to determine clinical remission status and treated as not meeting clinical remission.

- 6) The total PRO2 score for a specific visit is the sum (rounded to the nearest integer) of liquid or very soft stool subscore (without rounding)  $\times$  2 and abdominal pain subscore (without rounding)  $\times$  5 within the analysis window as defined in Section 3.8.2. If either subscore is missing, no imputation will be done, and the subject will be considered as having insufficient data to determine clinical remission status and treated as not meeting clinical remission by total PRO2 score.

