**Table 6-1. Definitions of Selected Efficacy Endpoints**

Study	Type	Endpoint	Definition
Induction	EU: secondary Non-EU: Co-primary	Clinical remission by CDAI at Week 10	CDAI score < 150 points at Week 10
Induction	Co-primary	Endoscopic response at Week 10	≥ 50% reduction from baseline in total SES-CD score at Week 10 based on central reading
Induction	EU: co-primary Other: Secondary	Clinical remission by PRO2 at Week 10	Abdominal pain score ≤ 1 (on a scale of 0 to 3) and liquid or very soft stool (Bristol stool scale type 6 or 7) frequency ≤ 3 at Week 10
Induction	Secondary	Clinical response by CDAI at Week 10	Reduction in CDAI score from Induction baseline by at least 100 points or CDAI score < 150 at Week 10
Induction	CCI	CCI	CCI
Induction	EU: Secondary Non-EU: CCI	Both clinical remission by PRO2 and endoscopic response at Week 10	Clinical remission by PRO2 and endoscopic response at Week 10 combined into a single endpoint on a patient level
Induction	CCI	CCI	CCI
Induction	CCI	CCI	CCI
Induction	CCI	CCI	CCI
Maintenance	Co-primary	Clinical remission by CDAI at Week 58	CDAI score < 150 points at Week 58

Study	Type	Endpoint	Definition
Maintenance	Co-primary	Endoscopic response at Week 58	≥ 50% reduction from Induction baseline in total SES-CD score at Week 58 based on central reading
Maintenance	Secondary	Clinical remission by PRO2 at Week 58	Abdominal pain score ≤ 1 (on a scale of 0 to 3) and liquid or very soft stool (Bristol stool scale type 6 or 7) frequency ≤ 3 at Week 58
Maintenance	Secondary	Clinical response by CDAI at Week 58	Reduction in CDAI score from Induction baseline by at least 100 points or CDAI score < 150 at Week 58
Maintenance	Non-EU: secondary	Sustained clinical remission by CDAI at Weeks 10 and 58	Clinical remission by CDAI at both Week 10 and Week 58
Maintenance	Non-EU: secondary	6-month Corticosteroid-free clinical remission by CDAI at Week 58	Clinical remission by CDAI with no corticosteroid use for the indication of CD for at least 6 months prior to Week 58 among subjects who are on corticosteroid at maintenance baseline (baseline of Maintenance Study). Subjects who weaned off steroids but required re-initiation within 6 months prior to Week 58 assessment will be considered to have not met this endpoint.
Maintenance	Secondary	Sustained clinical remission by PRO2 at Weeks 10 and 58	Clinical remission by PRO2 at both Week 10 and Week 58

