#### **6.1.1. Calculation of CDAI and PRO2 Scores**

The CDAI system is a composite index of 8 disease activity variables with scores ranging from 0 to over 600 based upon a composite of symptoms (eg, abdominal pain), signs (the presence of abdominal mass and weight), laboratory values (eg, hematocrit), and physician assessment amongst others. The CDAI has 3 PRO components: liquid or very soft stool frequency, abdominal pain, and general wellbeing. The clinical remission by CDAI endpoint is defined by the total CDAI score, calculated as a weighted sum of all 8 component subscores. If subjects have 3 or more of the 8 component subscores missing, then the subjects will be considered as having insufficient data to determine response status and their total CDAI score will be considered missing. If subjects have 1 or 2 CDAI components missing, then the missing component will be imputed by the LOCF method using the previous valid component score from the most recent analysis visit (ie, use the component score from Week 6 for missing

component at Week 10, or use the component score from Week 50 for missing component at Week 58. Scores from other post Induction baseline visits will not be used). If the component score from the most recent analysis visit is also missing, the missing value will be imputed with the corresponding component score at Induction baseline.

The PRO2 has 2 patient reported outcome components: liquid or very soft stool frequency subscore and abdominal pain subscore. If either subscore is missing, no imputation will be done, and the subject will be considered as having insufficient data to determine clinical remission status by PRO2 (or total PRO2 score) and treated as not meeting clinical remission. The clinical remission by PRO2 (or total PRO2 score) is defined by the PRO2 subscores as specified in [Table 6-1](#).

For further information on the CDAI/PRO2 and calculation rules at screening and post-screening, reference is made to [Appendix 3](#).

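### One blank complication item makes the SAP overwrite the recorded items with an earlier visit's component, so the CDAI can contradict what was recorded at Week 10 or Week 58

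*SAP*

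**What the plan says.** Table 13-1 in SAP Appendix 3 scores complications as a count ("Number of listed complications"): six separate items at 20 points each.

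For post-screening visits, Appendix 3 item 5 states: "If at least 1 out of the 6 complications under the complication component is missing, then the complication component will be considered missing". Section 6.1.1 and item 5a continue: "If subjects have 1 or 2 CDAI components missing, then the missing component will be imputed by the LOCF method". The source visit is fixed. For the induction endpoint the instruction is "use the component score from Week 6 for missing component at Week 10". The maintenance endpoint has its own instruction, with an eight-week gap: "use the component score from Week 50 for missing component at Week 58". If that component is missing too, "the missing value will be imputed with the corresponding component score at Induction baseline". Table 6-4 builds the same carry-forward into the primary estimand.

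The limit is: "If subjects have 3 or more of the 8 CDAI components missing, then the subjects will be considered as having insufficient data". Such a subject has no CDAI and counts as not in remission.

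The endpoint affected is "CDAI score < 150 points at Week 10" and its Week 58 counterpart.

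**The concern.** The rule lets an older value override data recorded at the endpoint visit. A subject with five of six complications recorded at Week 10 is scored on what was seen four weeks earlier. At Week 58 the carried value is eight weeks old, or more than a year old if it falls back to baseline.

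This sits in the primary derivation. CDAI remission is the clinical co-primary endpoint outside the EU and a key secondary endpoint in the EU analysis. The same total feeds CDAI response, sustained and corticosteroid-free CDAI remission, and the end-of-induction criteria in SAP 6.5.

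The rule also departs from the SAP's handling of partial data elsewhere. Diary components are calculated from as few as four evaluable days (Appendix 3). SES-CD keeps the segments that were read and imputes only the missing one (section 6.1.2).

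**Working it through.** **Inputs.** 20 points per complication, six items (Table 13-1); remission if CDAI < 150 (Table 6-1); 220 per arm, CDAI remission 45% vs 25%, endoscopic response 25% vs 10%, two-sided 0.05, stated power 97% (SAP 1.3, non-EU).

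**1. When the score contradicts the record.** Let x be the sum of the other seven components, r the number of complications recorded present when one item is blank, and m the number carried forward.
- The SAP scores x + 20m.
- The true total is either x + 20r or x + 20(r + 1).
- Remission is credited although the record rules it out when x + 20m < 150 ≤ x + 20r.
- Remission is denied although the record proves it when x + 20(r + 1) < 150 ≤ x + 20m.

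| x | r | m | SAP total | Possible true total | Result |
|---|---|---|---|---|---|
| 130 | 2 | 0 | 130 | 170 or 190 | remission credited wrongly |
| 130 | 1 | 0 | 130 | 150 or 170 | remission credited wrongly |
| 120 | 0 | 2 | 160 | 120 or 140 | remission denied wrongly |
| 130 | 0 | 2 | 170 | 130 or 150 | depends on the blank item |

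In the last two rows complications are scored 40 although the recorded items cap them at 20.

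**2. How often status changes, given one blank item.** The documents give no data, so this is an illustrative simulation. It assumes per-item prevalence of 5–20% at Week 6 and 5–15% at Week 10, latent correlation between visits of 0.5–0.8, and CDAI without complications distributed N(150, 70).
- Remission status is wrong in 4.2–8.8% of affected subjects under the rule, against 0.8–2.2% if only the blank item is carried forward.
- Crossing all the settings widens the range under the rule to about 3–11%.
- Centring the distribution at 190, nearer the planned placebo remission rate, lowers 4.2–8.8% to roughly 3–6%.

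**3. Subjects per arm.** Assume 1–5% of subjects have one blank item.
- Lower end: 220 × 0.01 × 0.042 = 0.09.
- Upper end: 220 × 0.05 × 0.088 = 0.97.
- With the wider 3–11%: 220 × 0.01 × 0.03 = 0.07 to 220 × 0.05 × 0.11 = 1.2.
- With item-level carry-forward: 220 × 0.01 × 0.008 = 0.02 to 220 × 0.05 × 0.022 = 0.24.

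**4. Power.** The plan's figure reproduces to within about a point: 0.9937 × 0.9869 = 98.1% (pooled normal approximation), or 97.4% with continuity correction. As a deliberately harsh case, let a fraction q of all non-remitters in both arms be scored as remitters, so that the rates become 0.25 + 0.75q and 0.45 + 0.55q.

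| q | Placebo | 200 mg | Difference (points) | Overall power |
|---|---|---|---|---|
| 0 | 25.00% | 45.00% | 20.0 | 98.1% |
| 1% | 25.75% | 45.55% | 19.8 | 97.9% |
| 2% | 26.50% | 46.10% | 19.6 | 97.8% |
| 5% | 28.75% | 47.75% | 19.0 | 97.3% |

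Even at q = 5% the loss is 98.1 − 97.3 = 0.8 points, and step 3 implies far less misclassification than that.

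**The case against.** The strongest reply is that this hardly matters. The rule is explicit, prespecified and identical across arms, and step 3 gives about one subject per arm at most. That stands, and it sets the grade of the point.

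Single blanks may also be rare. The protocol has CDAI calculated centrally after electronic capture of all components. At COVID-19 virtual visits, SAP 6.1.3 allows only anti-diarrheal use, hematocrit and weight to be done remotely, so complications would be missing as a whole and the fix would change nothing. This is plausible, but neither document says that each complication item is a mandatory field, and item 5 itself provides for a single missing item.

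The sensitivity analysis (Estimand 2, SAP 6.2.5.2) replaces carry-forward with multiple imputation and adds a tipping-point analysis, so it would show whether the result leans on carried values. It treats the whole CDAI as missing if any component is missing, however, so it does not use the recorded complication items either.

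The SAP has another all-or-nothing rule: fewer than four evaluable diary days makes a diary component missing. True, but three diary days do not bound a weekly sum as tightly as five of six items bound the complication count.

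Two stronger readings are tempting:
- A reader might infer that the rule inflates remission or favours filgotinib. The documents do not support this: errors run both ways and nothing ties blank items to treatment. At 20% prevalence at Week 6 and 15% at Week 10 (correlation 0.5), the simulation gives 5.9% wrongly denied against 2.8% wrongly credited.
- A reader might infer CDAI errors of 100 points or more. That is the arithmetic limit (5 × 20 = 100 recorded points dropped), but it needs about five complications at one visit and none at the other. It occurred in at most about 0.06% of affected simulated subjects. One of the six items, other fistula, also overlaps an entry exclusion (Protocol 4.2.2, criterion 6c).

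**Conclusion.** The point holds as a flaw in the endpoint derivation with a small expected effect on the trial. The rule can assign a remission status that data recorded at the same visit exclude, and no planned analysis uses those data.

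The estimate of about 0.1 to 1.0 misclassified subjects per 220-subject arm rests on two assumptions the documents do not supply: that 1–5% of subjects have one blank item, and the simulation inputs in step 2. The power effect is under one point even with much heavier misclassification. The demonstration that status can contradict the record rests on neither assumption, because it follows from the 20-point weight and the 150 threshold.

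This does not call the planned power or the co-primary conclusion into question. It is worth correcting because the correction is cheap and brings the rule into line with how the SAP treats diary days and SES-CD segments.

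**What to change.** In Appendix 3, replace the sentence on complications in item 5 with text to this effect:

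- Recorded complication items are kept. Only blank items are carried forward, from the visit allowed in item 5a: Week 6 for Week 10, Week 50 for Week 58, otherwise Induction baseline.
- If all six items are blank, the existing component-level carry-forward applies unchanged.
- A complication component with any blank item still counts as missing for the rule on three or more of the eight components and for the trigger of the Estimand 2 imputation in section 6.2.5.2.

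The last clause matters. Declaring the component missing only when all six items are blank would loosen the three-component safeguard and let carried-forward items into Estimand 2. The restriction of carry-forward to two source visits, which the SAP revision history attributes to regulatory feedback, is untouched. Section 6.1.1 and Table 6-4 need a matching cross-reference.

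The cost is a short text change and a small change to the derivation program, with no new data. Each blank item still takes a carried-forward value, with an error of at most 20 points per blank item. The change should be made before unblinding so that it cannot look data-driven.
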